6.2.7 ACCEPTABLE CONCOMITANT MEDICATIONS

All treatments that the Principal Investigator considers necessary for a subject's welfare may be administered at the discretion of the Principal Investigator in keeping with the community standards of medical care. All concomitant medication will be recorded on the eCRF including all prescription, over-the-counter (OTC) products, herbal supplements, and IV medications and fluids. If changes occur during the trial period, documentation of drug dosage, frequency, route, and date should also be included on the eCRF.

All concomitant medications received within 28 days prior to the screening visit and up to 30 days after the last dose of trial treatment should be recorded. Concomitant medications administered 30 days after the last dose of trial treatment should be recorded for SAEs and ECIs.

6.2.8 PERMITTED THERAPIES: SRT

For patients that are deriving clinical benefit from protocol treatment, but having evidence of progression in brain lesions that are amenable to SRS, treatment with SRS is allowed and patients can remain on systemic therapy. Patients will be censored for brain metastasis response unless one measurable lesion remains unirradiated. Patients will continue to be monitored for intracranial PFS.

6.2.9 PERMITTED THERAPY FOR BRAIN EDEMA

Patients that develop neurologic symptoms suspected to be secondary to brain edema are allowed to receive steroids as clinically indicated.

6.2.10 PERMITTED THERAPY: BRAIN SURGERY

Patients that develop an indication for brain surgery will be managed as clinically indicated. They will be assessed post-operatively in the setting of the MD Anderson Brain Metastasis Clinic (or similar multi-disciplinary setting) to determine whether resuming systemic therapy on protocol is warranted. The same dose interruptions and treatment resumption criteria that apply to SRT will apply to neurosurgical intervention as well.

7.0 PROHIBITED CONCOMITANT MEDICATIONS

As stated for the exclusion criteria in Section 5.2, subjects must not have had chemotherapy, radiotherapy (other than palliative radiotherapy delivered in a normal organ-sparing technique), major surgery, or received another investigational agent within 14 days before the start of trial treatment.

The following treatments must not be administered during the trial:

- Immunotherapy including interferon, immunosuppressive drugs (for example, chemotherapy or systemic corticosteroids except for short term treatment of allergic reactions, endocrine replacement therapy at low dose prednisone [≤ 10 mg daily] or equivalent, or for the treatment of irAEs or other appropriate short term steroid use), or other experimental pharmaceutical products. Short term administration of systemic steroid or other immunosuppressant such as infliximab or mycophenolate (that is, for allergic reactions or the management of irAEs) is allowed. Steroids with no or minimal systemic effect (topical, inhalation) are allowed.
- Adefovir.
- Prophylactic use of corticosteroids for infusion related reactions is prohibited.
- Any live vaccine therapies for the prevention of infectious disease. Administration of inactivated vaccines is allowed (for example, inactivated influenza vaccines or approved SARS-COV-2 vaccines).
- Vaccines will be allowed and will require one week between administration and treatment.

If the administration of a non-permitted concomitant drug becomes necessary during the trial, the subject will be withdrawn from trial treatment (the Principal Investigator may be contacted to discuss whether the BINTRAFUSP ALFA must be discontinued).

Medications other than those specifically excluded in this trial (as outlined in this section) may be administered for the management of symptoms associated with the administration of Bintrafusp Alfa (M7824) as required. These might include analgesics, anti-emetics, antihistamines, diuretics, anti-anxiety medications, and medication for pain management, including narcotic agents.

Any additional concomitant therapy that becomes necessary during the trial and any change to concomitant drugs must be recorded in the corresponding section of the eCRF (Prometheus) and medical record, noting the name, dose, duration, and indication of each drug.

The following non-drug therapies must not be administered during the trial (and within 28 days before the start of trial treatment):

- Major surgery (excluding prior diagnostic biopsy).Herbal remedies with immunostimulating properties (for example, mistletoe extract) or known to potentially interfere with major organ function (for example, hypericin)
- Subjects should not abuse alcohol or other illicit drugs during the trial

Drugs known to prolong the QT interval must be used with caution if they cannot be avoided. The list of the drugs in question is given at the following web address: <http://crediblemeds.org/everyone/composite-list-all-qtdrugs/?rf>All>

Furthermore, caution should be exercised when starting or increasing the dose of any medication that is considered to be associated with muscle toxicity (e.g., 3-Hydroxy-3-Methylglutaryl- Coenzyme A [HMG CoA] reductase inhibitors [statins]).

Interactions

- Pimasertib is a substrate of Cytochrome P450 (CYP) Isoforms CYP3A4 and CYP2C19, and may possibly inhibit CYP2C9.

Based on this, it was concluded that concomitant administration with the following drugs should be used with caution or avoided if possible:

- Strong inhibitors of CYP3A4
- Strong inducers of CYP3A4
- Strong inhibitors of CYP2C19
- Substrates of CYP2C9 with a narrow therapeutic index

A list of drugs that should be used with caution or avoided is presented can be found here:

<https://drug-interactions.medicine.iu.edu/Main-Table.aspx>

SPECIAL PRECAUTIONS

As a routine precaution, subjects all enrolled in this trial must be observed for 2 hours in the CTRC post end of infusion, in an area with resuscitation equipment and emergency agents at least for the first two doses of treatment with Bintrafusp Alfa (M7824). If no medical problems arise during the first two treatments, then the 2 hour observation period does not need to continue starting with the third dose of treatment. At all times during Bintrafusp Alfa (M7824) treatment, immediate emergency treatment of an infusion-related reaction or a severe hypersensitivity reaction according to institutional standards must be assured. In order to treat possible anaphylactic reactions, for instance, dexamethasone 10 mg and epinephrine in a 1:1000 dilution or equivalents should always be available along with equipment for assisted ventilation.

Infusion of Binrafusp Alfa (M7824) will be stopped in case of Grade ≥ 2 hypersensitivity, inflammatory response, or anaphylactic reaction. The treatment recommendations for infusion-related reactions and severe hypersensitivity reactions according to the NCI are outlined in Section 6.2.3.

Principal Investigators should also monitor subjects closely for potential irAEs (described in Section 6.2.3), which may become manifest after several weeks of treatment. Such events may consist of persistent rash, diarrhea and colitis, autoimmune hepatitis, arthritis, glomerulonephritis, cardiomyopathy, or uveitis and other inflammatory eye conditions.

8.0 SCHEDULE OF ASSESSMENTS

TABLE 3 SCHEDULE OF ASSESSMENTS

Trial Period:	Screening Phase	Treatment Cycles ^a										End of Treatment	Post-Treatment		
		To be repeated beyond 8 cycles				Discontinuation				Safety Follow-up	Follow Up Visits ^b				
Treatment Cycle/Title:	Screening	C1 D1	C1 D15	C2 D1	C2 D15	3	4	5	6	7	8				
Scheduling Window (Days):	-28 to -1			± 3		± 3	± 3	± 3	± 3	± 3	± 3	At time of Discontinuation	30 days post discontinuation ± 7	Every 6 weeks post discontinuation ± 7	Every 12 weeks ± 7
Administrative Procedures															
Informed Consent	X														
Inclusion/Exclusion Criteria	X														
Demographics and Medical History	X														
Prior and Concomitant Medication Review	X	X	X	X	X	X	X	X	X	X	X	X			
Trial Treatment Administration ^c		X	X	X	X	X	X	X	X	X	X				

Trial Period:	Screening Phase	Treatment Cycles ^a										End of Treatment	Post-Treatment			
		To be repeated beyond 8 cycles														
Treatment Cycle/Title:	Screening	C1	C1	C2	C2	3	4	5	6	7	8	Discontinuation	Safety Follow-up	Follow Up Visits ^b	Survival Follow-Up ^p	
		D1	D15	D1	D15			± 3	± 3	± 3	± 3					
Scheduling Window (Days):	-28 to -1												At time of Discontinuation	30 days post discontinuation ± 7	Every 6 weeks post discontinuation ± 7	Every 12 weeks ± 7
Post-study anticancer therapy status															X	X
Survival Status																X
Clinical Procedures/Assessments																
Review Adverse Events			X	X	X	X	X	X	X	X	X	X	X	X	X	X
Physical Examination	X		X	X	X	X	X	X	X	X	X	X	X			X
Vital Signs, Weight, and Height ⁿ	X		X	X	X	X	X	X	X	X	X	X	X			X
Electrocardiogram (12-Lead ECGs)	X															
ECHO/MUGA	X			X			X		X		X		X			
Ophthalmological Exam ^l	X						X		X		X		X			

Trial Period:	Screening Phase	Treatment Cycles ^a										End of Treatment	Post-Treatment		
		To be repeated beyond 8 cycles											Safety Follow-up	Follow Up Visits ^b	Survival Follow-Up ^p
Treatment Cycle/Title:	Screening	C1 D1	C1 D15	C2 D1	C2 D15	3	4	5	6	7	8	Discontinuation			
		± 3	± 3	± 3	± 3	± 3	± 3	± 3	± 3	± 3	± 3	At time of Discontinuation			
Scheduling Window (Days):	-28 to -1												30 days post discontinuation ± 7	Every 6 weeks post discontinuation ± 7	Every 12 weeks ± 7
ECOG Performance Status	X	X	X	X	X	X	X	X	X	X	X	X		X	X
Neuro-function (NANO)	X	X		X		X	X	X	X	X	X	X			
Neuropsych Testing ^o /Neurocognitive Testing	X					X									
Laboratory Procedures/Assessments: analysis performed by LOCAL laboratory															
Pregnancy Test – Urine or Serum -HCG ^d	X			X		X	X	X	X	X	X	X			
Coagulation ^e	X														
CBC with Differential ^k	X	X	X	X	X	X	X	X	X	X	X	X		X	
CMP ^m	X	X	X	X	X	X	X	X	X	X	X	X		X	
Urinalysis	X			X		X	X	X	X	X	X	X			

Trial Period:	Screening Phase	Treatment Cycles ^a								End of Treatment	Post-Treatment				
		To be repeated beyond 8 cycles				Discontinuation					Safety Follow-up	Follow Up Visits ^b	Survival Follow-Up ^p		
Treatment Cycle/Title:	Screening	C1 D1	C1 D15	C2 D1	C2 D15	3	4	5	6	7	8				
Scheduling Window (Days):	-28 to -1			± 3		± 3	± 3	± 3	± 3	± 3	± 3	At time of Discontinuation	30 days post discontinuation ± 7	Every 6 weeks post discontinuation ± 7	Every 12 weeks ± 7
Lactate dehydrogenase (LDH)	X			X		X	X	X	X	X	X	X			
T3, FT4 and TSH	X	X				X		X		X		X			
Creatinine Phosphokinase	X	X		X		X	X	X	X	X	X	X			
HIV, HBV, HCV Testing	X														
Efficacy Measurement															
Tumor Imaging & Assessment of disease: MRI ^f	X			X		X	X	X	X	X	X	X			
Tumor Imaging & Assessment of disease: CT's ^f	X					X		X		X					
Tumor Biopsies/Archival Tissue Collection/Correlative Studies Blood															

Trial Period:	Screening Phase	Treatment Cycles ^a								End of Treatment	Post-Treatment				
		To be repeated beyond 8 cycles				Discontinuation					Safety Follow-up	Follow Up Visits ^b	Survival Follow-Up ^p		
Treatment Cycle/Title:	Screening	C1 D1	C1 D15	C2 D1	C2 D15	3	4	5	6	7	8				
Scheduling Window (Days):	-28 to -1			± 3		± 3	± 3	± 3	± 3	± 3	± 3	At time of Discontinuation	30 days post discontinuation ± 7	Every 6 weeks post discontinuation ± 7	Every 12 weeks ± 7
Archival Tissue ^g	X														
Serial Biopsy ^h	X			X			X								
Blood/Tissue Collection	X			X		X	X	X	X	X	X				
Correlative Studies ^j	X			X			X				X				
PK and ADA		X		X		X		X			X		X		
CSF ⁱ (optional)	X	X				X									

- a Cycles are 4 weeks (28 days) in duration
- b Patients who discontinue trial treatment for reasons other than disease progression will move into the Follow-Up phase. Patients will be seen every 6 weeks for the first year, then every 12 weeks thereafter up to 2 years.
- c M7824 1200 mg every 2 weeks. Pimasertib will be administered at 60mg twice daily. (30 to 60 mg depending on phase)
- d See Page 78 if a woman of child-bearing potential becomes pregnant while on study. Negative pregnancy test within 3 days prior to initiation of dosing and continuation of birth control for 120 days after last dose of drug.
- e Prothrombin time/International Normalized Ratio, Activated Partial thromboplastin time.
- f MRI Scan will be performed every 4 weeks for the first 16 weeks, then every 8 weeks until progression or discontinuation of study treatment, whichever comes later. Imaging window is \pm 7 days. If scans performed within 4 weeks of discontinuation, repeat scans are not required.
CT-CAP or PET-CT will be performed every 8 weeks until progression or discontinuation of study treatment, whichever comes later. Imaging window is \pm 7 days. If scans performed within 4 weeks of discontinuation, repeat scans are not required.
Please note that if an MRI, CT chest/abdomen/pelvis or PET-CT is not already performed as standard of care per Schedule of Assessments in Section 8.1.4, the investigator may choose to perform either or both procedures for assessing progress of the patient.
- g Obtain archival only if tissue is post PD-1 exposure for melanoma and lung cancer patients. See Section 8.7.1 for additional details.
- h Patients with biopsiable extracranial disease may have tissue collected. See Section 8.8.
- i Cerebrospinal Fluid may be obtained if testing for LMD. See section 8.7.3 for additional details.
- j See Section 8.7.
- k CBC & CMP is done every 2 weeks (+/- 7 days) prior to infusion.
- l Patients will have ophthalmological evaluation at baseline and every 12 weeks. See section 8.3.
while receiving protocol therapy
- m Serum chemistry includes the tests listed (glucose, BUN, creatinine, sodium, potassium, magnesium, chloride, bicarbconate, calcium, phosphorus, total and direct bilirubin, ALT, AST, ALP, LDH, total protein, albumin, CPK, and uric acid). CMP is done every 2 weeks prior to infusion.
- n Height only taken at Screening
- o There will also be a Neurocognitive exam at the 3-month mark
- p A follow up call will be done at 90 days to assess patient safety.

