4.1.2 PHASE II PRIMARY OBJECTIVE

- Time to intracranial progression (defined as progression of existing lesions by modified RECIST 1.1) lesions and development of new
- Overall survival.

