4.2 SECONDARY OBJECTIVES

- Intracranial progression 4, 8, 12, 16 weeks and every 8 weeks thereafter.
- Intracranial objective response rate as measured by RANO-BM, iRANO, and RECIST 1.1.
- Time to second intracranial progression after Salvage SRS
- Overall survival rate at 24, 52 and 68 weeks.
- Frequency of grade 3+ intracranial toxicities at 4, 12, 24, 36, 52, and 68 weeks. Frequency of extracranial progression and response rate at 8, 16, 24, every 8 weeks.
- Frequency of neurocognitive decline 12, 24, 36 weeks (optional). Changes in neurocognitive function and health-related quality of life.
- Dose, duration and frequency of steroid use for symptomatic management.
- Evaluation of safety and tolerability of pimasertib/bintrafusp alfa combination

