8.1.4 RESPONSE ASSESSMENT

MRI of the brain will be the primary radiological method of disease assessment using modified RECIST 1.1. Treatment decisions will be made according to modified RECIST 1.1 while other measurement criteria will be utilized as secondary endpoints including iRANO criteria (See Appendix 1). Quantitative imaging changes on multiparametric MRI will be captured to determine early biomarkers of immune response. Standard of care brain MRI with intravenous gadolinium contrast and contrast enhanced CT chest/abdomen/pelvis or PET-CT, as clinically indicated, will be used to assess both intracranial and extracranial disease at Screening and every 4 weeks for the first 12 weeks, then every 8 weeks for the first year, then every 12 weeks until progression or discontinuation of study treatment, whichever comes

later. Imaging window is \pm 7 days. If scans performed within 4 weeks of discontinuation, repeat scans are not required. Screening MRI and CT assessments must occur within 28 days prior to day 1.

If an MRI, CT chest/abdomen/pelvis or PET-CT is not already performed as standard of care per Schedule of Assessments in Section 8.0, the principal investigator may choose to perform either or both procedures for assessing the progress of the patient.

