8.15 POST STUDY DRUG FOLLOW UP

In this study, clinical benefit rate is the primary endpoint of the study. Post study follow-up is of critical importance and is essential to preserving subject safety and the integrity of the study.

Subjects who discontinue study drug must continue to be followed for collection of outcome and/or survival follow-up data as required by phone every 12 weeks until death or the conclusion of the study.

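### Required brain MRI runs to the later of a progression of unstated site and drug stop, so patients who stop for extracranial progression, or who stop after salvage SRS, have no further required scan for the intracranial endpoints

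*Combined protocol and SAP*

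**What the plan says.** Section 4.1.2 makes time to intracranial progression, by modified RECIST 1.1, a phase II primary endpoint alongside overall survival. Section 4.2 lists "Time to second intracranial progression after Salvage SRS" as a secondary objective.

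The scans behind both are governed by two places.

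- **Table 3, footnote f:** brain MRI every 4 weeks for 16 weeks, "then every 8 weeks until progression or discontinuation of study treatment, whichever comes later". A separate sentence gives body CT or PET-CT the same end point.
- **Section 8.1.4:** one sentence covers brain MRI and body imaging together, "every 4 weeks for the first 12 weeks, then every 8 weeks for the first year, then every 12 weeks until progression or discontinuation", again with the later of the two events deciding.

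Neither place says intracranial progression. Three others describe what happens after drug stop.

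- **Table 3, footnote b:** "Patients who discontinue trial treatment for reasons other than disease progression will move into the Follow-Up phase".
- **Table 3, MRI row:** marks at screening, cycles 2 to 8 and discontinuation, with none readable in the post-treatment columns.
- **Section 8.15:** patients off drug are followed for outcome or survival "as required by phone every 12 weeks until death or the conclusion of the study".

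For analysis, section 9.2 names death as the only competing risk. Section 9.3.2 censors patients without intracranial progression at their last follow-up, and leaves it optional to treat extracranial progression as a competing event.

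**The concern.** A primary endpoint that only a brain scan can establish radiographically needs a scan rule tied to that endpoint. Here the rule is tied to a progression of unstated site and to drug stop. A patient whose body disease progresses while the brain is controlled, and who then stops drug, satisfies both conditions at once. Required MRI ends before the primary endpoint has occurred.

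The second-progression objective has a related problem. Its clock starts after a first intracranial progression, so one of the two conditions is already met and drug stop alone ends required MRI.

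At stake are the number of intracranial events observed among 30 patients and, depending on how the unscanned time is handled, the validity of the estimate meant to inform later studies. Scans not collected cannot be recovered at analysis.

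**Working it through.** **Reading the rule.** Let P be progression and S drug stop. Required MRI ends at the later of P and S.

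| Patient | Required brain MRI |
|---|---|
| Stops drug for extracranial progression, brain controlled | Ends at S; footnote b keeps the patient out of the Follow-Up visits, leaving phone contact |
| Stops for toxicity without progression | Continues under footnote f to P, although Table 3 marks no post-treatment MRI; ends even if P is extracranial |
| Treated beyond progression (8.10) | Continues while on drug |
| Salvage SRS, stays on drug (6.2.8) | Continues while on drug |
| Salvage SRS, then stops drug before second progression | Ends at S |

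The first and last rows are the gap. Section 6.2.8 says monitoring for intracranial PFS continues after SRS but sets no off-drug scans. Appendix 2 accepts only contrast-enhanced MRI for intracranial lesions, so a phone call cannot establish radiographic progression.

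**Size.** The plan gives no progression or survival assumption for phase II, so there is no figure to reproduce. The 30 patients come from section 9.2 (6 + 24). The rest is assumed: exponential times; median intracranial progression 4 months, extracranial 4 or 8, death 7 or 10; drug and MRI both stop at extracranial progression.

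Hazards per month: a = ln2/4 = 0.1733; e = ln2/4 = 0.1733 or ln2/8 = 0.0866; d = ln2/7 = 0.0990 or ln2/10 = 0.0693. Let s = a + e + d, and let m multiply the brain hazard after drug stop.

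- Seen by time T: (a/s)(1 − exp(−sT)).
- Missed by T: ∫₀ᵀ e·exp(−su)·[ma/(ma+d)]·[1 − exp(−(ma+d)(T−u))] du.
- With m = 1, seen plus missed equals [a/(a+d)](1 − exp(−(a+d)T)).

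Worked case: extracranial 4, death 10, m = 1, T = 12.

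- Seen: 0.4167 × (1 − 0.0068) = 0.4138, or 12.4 of 30.
- All: 0.7143 × (1 − 0.0544) = 0.6754, or 20.3 of 30.
- Missed: 30 × (0.6754 − 0.4138) = 7.8.

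| Extracranial / death median (months) | Seen by 12 months, of 30 | Missed: m = 0.5 | m = 1 | m = 2 |
|---|---|---|---|---|
| 4 / 10 | 12.4 | 5.3 | 7.8 | 10.0 |
| 4 / 7 | 11.6 | 4.5 | 6.8 | 8.8 |
| 8 / 10 | 15.5 | 3.2 | 4.8 | 6.1 |
| 8 / 7 | 14.3 | 2.7 | 4.1 | 5.4 |

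For m between 1 and 2, the loss is 4.1 to 10.0 of 30.

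**Bias.** The quantity is the 6-month cumulative incidence of intracranial progression with death competing. Censoring at the last MRI, taken as the time of extracranial progression, gives [a/(a+d)](1 − exp(−6(a+d))) whatever m is. If the patient instead counts as brain-progression-free through phone contact beyond month 6, the result is (a/s)(1 − exp(−6s)).

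| Extracranial / death | True: m = 0.5 | m = 1 | m = 2 | Censored at last MRI | Carried on by phone |
|---|---|---|---|---|---|
| 4 / 10 | 0.480 | 0.548 | 0.629 | 0.548 | 0.382 |
| 4 / 7 | 0.450 | 0.512 | 0.588 | 0.512 | 0.362 |
| 8 / 10 | 0.509 | 0.548 | 0.595 | 0.548 | 0.453 |
| 8 / 7 | 0.477 | 0.512 | 0.556 | 0.512 | 0.427 |

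- **Last-MRI censoring:** no bias at m = 1. It understates by 4 to 8 points at m = 2 and overstates by about 4 to 7 points at m = 0.5.
- **Phone-date censoring:** at m = 1 it understates by 0.512 − 0.427 = 0.085 to 0.548 − 0.382 = 0.166, about 9 to 17 points.
- **Scale:** with complete data, a 95% half-width at 30 patients is 1.96 × √(0.548 × 0.452/30) = 0.178.

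**The case against.** **Progression in the MRI sentence may mean progression on MRI.** Footnote f gives MRI and CT separate sentences, so this reading is possible, and it would remove the gap for the primary endpoint. A reader might infer that the text says progression of any kind; it does not, it leaves the site open. But section 8.1.4 merges the modalities, footnote b excludes every patient who stops for progression, and the protocol writes intracranial elsewhere when it means it. The narrow reading also leaves second progression without required off-drug MRI.

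**The Table 3 grid is weak evidence.** This stands in part. The text was read from PDF, and the grid marks MRI at every cycle from 3 to 8 although footnote f moves to 8-weekly scans after week 16. Still, the CBC and CMP rows keep a post-treatment mark and the MRI row does not.

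**Many patients are still scanned.** This stands. A reader might infer that MRI ends at the earlier of the two events; the text says the later, so patients treated beyond progression or kept on drug after SRS stay on the schedule. If half of extracranial progressors continued drug, the loss would halve to about 2 to 5 of 30. Section 8.1.4 describes brain MRI as standard of care and allows discretionary scans, so some events would be found anyway. A reader might infer that second progression off drug cannot be observed; the documents support only that scans for it are not required. Section 8.13 encourages attendance at remaining visits, but the post-treatment visits carry no marked MRI.

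**A different estimand avoids the gap.** Intracranial progression as first event needs no scan after extracranial progression. Section 9.3.2 permits such an analysis only as an option, and section 9.2 names death alone.

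**Conclusion.** The gap is real. For patients who stop drug because of extracranial progression, the documents as written require no further brain MRI, and after salvage SRS the second-progression objective is in effect limited to patients still on drug.

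The loss of 4 to 10 events per 30 patients rests on the assumed medians, on every extracranial progressor stopping drug, and on a brain hazard 1 to 2 times as high afterwards. It falls to about 3 to 5 if that hazard halves.

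A reader might infer that the estimate must flatter the combination. The documents do not establish that for censoring at the last MRI: under independence only precision is lost, and under dependence the direction follows the brain hazard after stopping. The understatement that does hold under independence comes from section 9.3.2, if its last follow-up is a phone contact without a scan.

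This is a cheap improvement that should be made rather than a condition for the trial to proceed. Phase II is uncontrolled estimation for planning later studies, with no efficacy decision rule, and toxicity monitoring uses a 4-week window.

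**What to change.** 1. In footnote f and section 8.1.4, give brain MRI its own rule, separate from body CT. Results are collected until intracranial progression, or after salvage SRS until second intracranial progression, or until death or withdrawal of consent, regardless of extracranial progression or drug stop. At the least, record standard-of-care brain MRIs in the eCRF.
2. Align footnote b and the post-treatment columns of Table 3 with that rule. Reconcile the two MRI interval schedules while doing so: 4-weekly to week 16 in footnote f, to week 12 in section 8.1.4, with different later intervals.
3. In section 9.3.2, censor at the last evaluable brain MRI. This removes the phone-date understatement but not bias from dependence, so it does not replace items 1 and 2.

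The cost is amendment wording, longer imaging data collection and a few more scans in patients off drug. At a single centre where brain MRI is already described as standard of care, much of the data should exist.
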